8. RESEARCH METHODS

8.1. Study Design

This will be an observational COPD cohort study that will utilize the CPRD and the Salford EHR system – to compare selected cohorts with SLS.

For SLS, reference/index date is study entry. This will be matched in CPRD by the following algorithm:

1. Draw up a long-list of potentially eligible individuals in CPRD (patients who would be eligible at some point during the SLS recruitment phase).

2. For each individual:

- a. Randomly sample an entry date from full list of SLS entry dates.
- b. If patient is eligible at that entry date, then they will be included, accounting for relevant immortal time biases up to that entry date, otherwise, they will be excluded. Further details on methods of reducing immortal time bias (i.e left truncated at the entry date and survival modelling) will be outlined in the SAP.

First, the COPD populations in both Salford and in the wider CPRD (excluding Greater Manchester area) will be compared. Second, we will focus on comparisons between all patients enrolled in the SLS SOC arm versus a CPRD cohort that would have been eligible for SLS as per the inclusion and exclusion criteria.

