8.3.2. Exposure definitions

This is a binary comparison of COPD patients enrolled in the SLS and COPD patients in the CPRD. Hence the primary exposure of interest is whether a patient is enrolled in SLS (yes/no). A third grouping, COPD patients in Salford (who are not in SLS) will also be examined.

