8.4. Data sources

The three main data sources are SLS, CPRD and SIR.

The Salford Lung Study (SLS) is described in [14]. In brief, it is a pragmatic trial, carried out in Salford, UK, to evaluate the relative effectiveness and safety of RELVAR compared with SOC. There are two separate studies within the SLS; one for COPD and the other for asthma. For this protocol, the SLS data refers to SLS for COPD only.

WWEpi Project number: PRJ2282

The CPRD is a primary care database consisting of a subset of GP practices across the UK. This will be linked to Hospital Episode Statistics (HES), socio-economic status (SES) and Office of National Statistics (ONS) datasets. For brevity, the linked dataset will henceforth be referred to as CPRD.

The SIR is a comprehensive primary and secondary care database detailing healthcare contacts, diagnostic tests and prescriptions of all patients registered with a GP in Salford, UK.

There are a range of subsets and derivations of the data sources that will be considered for this study, listed here for clarity.

CPRD: CPRD – all practices, all COPD patients

CPRD-GM: CPRD – practices/patients in Greater Manchester only, all COPD patients

CPRD-xGM: CPRD – excluding practices/patients in Greater Manchester, all COPD patients

CPRD-GM-IC: CPRD – practices/patients in Greater Manchester only, COPD patients meeting SLS inclusion criteria only

CPRD-xGM-IC: CPRD – excluding practices/patients in Greater Manchester, COPD patients meeting SLS inclusion criteria only

SLS-E: SLS – all eligible. Not all of these are enrolled (some decline)

SLS: SLS - all enrolled

SLS-SOC: SLS – SOC arm only

SIR: SIR – all COPD patients

SIR-IC: SIR - COPD patients meeting SLS inclusion criteria only

In the CPRD, data linkage will be subject to a lag due to the delayed availability of HES and ONS data. Fully linked data will only be available up to a certain date when analyses are undertaken, and as such, primary analyses will be restricted to include SLS enrolled patients up to that date. Subsequent analyses will be conducted once linkage is available for the entire recruitment period. As capture of events of serious pneumonia (as defined in the context of this study) is dependent on records of hospitalisation, PO3 will be analysed when fully linked CPRD-HES data are available.

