Firstly, for descriptive purposes, we will measure the prevalence of the endpoints in a series of subgroups. For example, we will compare the COPD exacerbations in CPRD-xGM-IC with SLS, stratified by SES, gender, etc.

Secondly, we will take a multilevel modelling approach. For this we will combine the SLS and CPRD into one dataset (retaining an indicator of SLS membership). The hierarchies of the model will be patient -> GP practice -> local authority region (with SLS members being treated as a single distinct region) -> strategic health authority region. Strategic health authorities (population threshold of 1 million) are non-anonymised (named) regions. Local authority regions are below the population threshold so an anonymised LA marker will be available.

We will include all confounders and effect modifiers as covariates, with outcomes corresponding to the primary and secondary study outcomes (a separate model for each). Important fixed effects at the local authority level (for example, existence of community teams) will be incorporated into the model if these can be ascertained.

A final model will be selected via backward selection using AIC (Akaike Information Criterion). We will then examine the random effect of the SLS region in the context of the random effects for the other regions. Similar to the above, if the random effect of the SLS region falls outside the 2.5-97.5 percentile range, we will conclude that SOC SLS behaves unusually compared with the rest of the UK, and hence evidence of a Hawthorne effect.

PO3 will be carried out using the same approach as for PO2.

SO1 and SO2 (which pertain to comparing other endpoints, and sensitivity analyses of endpoint definition) will be carried out in the same way as PO2.

SO3 makes explicit the possible change in outcomes at commencement of SLS. We will compare outcome rates within Salford before and after the commencement of SLS, in a self-controlling case design. We will do the same thing within CPRD to control for UK-wide secular trends. This acts as sensitivity analysis to support PO2 (using controls distinct in time rather than in geography).

WWEpi Project number: PRJ2282

Additional work will take place exploring the development of methods for a framework of measuring representativeness; this is not within scope of this protocol and is described in Annex 2.1.

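### Section 8.7.1 names the PO2 analysis sets (carried to PO3, SO1 and SO2) inconsistently with the objectives and the protocol's own labels; read literally, RELVAR patients enter a comparison meant for the SOC arm only

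*Protocol*

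**What the plan says.** Section 8.4 of the protocol lists data-set labels so that analyses can be specified without ambiguity. Four matter here:

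- "SLS: SLS - all enrolled"
- "SLS-SOC: SLS – SOC arm only"
- "CPRD: CPRD – all practices, all COPD patients"
- "CPRD-xGM-IC: CPRD – excluding practices/patients in Greater Manchester, COPD patients meeting SLS inclusion criteria only"

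Section 8.7.1 then describes PO2 in two steps. In the descriptive step, "we will compare the COPD exacerbations in CPRD-xGM-IC with SLS, stratified by SES, gender, etc". For the multilevel model, "For this we will combine the SLS and CPRD into one dataset (retaining an indicator of SLS membership"). SLS members form one region of that model. If that region's random effect lies outside the 2.5 to 97.5 percentile range of the regional effects, the SOC patients of SLS are declared unusual and a Hawthorne effect is inferred. PO3, SO1 and SO2 follow the same approach.

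Section 8.3.2 sets the exposure: "Hence the primary exposure of interest is whether a patient is enrolled in SLS (yes/no"). Section 8.2.1 adds that the SLS data are taken without further restriction.

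The intended comparison is narrower. Section 8.1 describes "comparisons between all patients enrolled in the SLS SOC arm versus a CPRD cohort that would have been eligible for SLS".

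**The concern.** The labels in 8.4 are defined terms, and elsewhere in 8.7.1 they are used with their suffixes. The descriptive PO2 sentence takes care to write `CPRD-xGM-IC` but pairs it with `SLS`, the both-arms label. The model sentence then drops the suffix on both sides. A programmer working from 8.4 and 8.7.1 would load all enrolled SLS patients, and 8.3.2 would confirm that choice.

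The inference depends on this. The Hawthorne conclusion rests on the SLS region effect alone. If half or more of the patients in that region are on the trial medicine, the effect mixes a RELVAR treatment effect with any effect of being studied. A benefit of RELVAR could be reported as a Hawthorne effect, or an effect of RELVAR in the other direction could mask one. This touches two co-primary objectives, PO2 and PO3.

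**Working it through.** **Step 1. The SLS side, place by place.**

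| Place in the protocol | Who is on the SLS side |
|---|---|
| Objectives PO2 and PO3 | SOC arm |
| Abstract, Population | SOC arm |
| 8.1 Study design | SOC arm |
| 8.3.1 Outcome definitions | SLS rate in the SOC arm |
| 8.9 Limitations | Hawthorne effect assessable for the SOC comparison only |
| 8.7.1, conclusion drawn from the model | SOC patients of SLS |
| 8.7.1, descriptive step | `SLS`, i.e. all enrolled |
| 8.7.1, model data set | `SLS`, i.e. all enrolled |
| 8.3.2 Exposure | enrolled in SLS, yes or no |
| 8.2.1 | SLS used without restriction |

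The last four rows admit both arms and the first six do not. `SLS-SOC` is defined in 8.4 but used in none of the analyses of 8.7.1.

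**Step 2. Does another rule remove RELVAR patients?** Exclusion 4 in 8.2.2 removes patients randomised to RELVAR, but only from the restricted cohorts. Section 8.2.1 builds those in the Salford and CPRD populations and then names SLS separately as a third source. The exclusion therefore does not clearly reach the SLS data.

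**Step 3. Does the model adjust for arm?** The covariates in 8.3.3 do not include randomised arm. The medication groups include LABA with ICS but do not separate RELVAR, which section 6.1 describes as an ICS/LABA combination. A RELVAR effect would therefore load on the SLS region effect.

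**Step 4. Size on the SLS side.** The protocol gives no effect size, power or derived sample size for this comparison, so there is no figure to reproduce. It also states neither the allocation ratio nor a RELVAR/SOC rate ratio; both are assumptions here. With RELVAR share *s* and rate ratio RR,

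pooled SLS rate / SOC rate = (1 − *s*) + *s* × RR.

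At *s* = 0.5 this is (1 + RR)/2:

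- RR 0.8: (1 + 0.8)/2 = 0.90
- RR 0.9: (1 + 0.9)/2 = 0.95
- RR 1.0: 1.00, no bias
- RR 1.1: (1 + 1.1)/2 = 1.05

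At *s* = 0.67:

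- RR 0.8: 0.33 + 0.67 × 0.8 = 0.866
- RR 0.9: 0.33 + 0.67 × 0.9 = 0.933
- RR 1.0: 1.00

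Whether such a shift takes the region outside the percentile range depends on the spread of the local authority effects, which the protocol does not give.

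**Step 5. The CPRD side.** The model sentence says `CPRD`. In 8.4 that is both a label (all practices, all COPD patients) and the short name of the linked data source. Neither meaning carries an eligibility or geographic limit. However, 8.1 calls for a CPRD cohort eligible for SLS, 8.2 places the CPRD group outside Greater Manchester, 8.2.1 makes that an inclusion criterion even for the broad CPRD cohort, and the descriptive step uses `CPRD-xGM-IC`. The document offers no rates from which to quantify an effect.

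**The case against.** The strongest reply is that `SLS` and `CPRD` are also plain names of data sources, so combining them may mean no more than merging two files. The protocol fixes the population elsewhere: the abstract, the objectives, 8.1 and 8.3.1 all say the SOC arm, and the model's conclusion is worded for SOC patients. PO1 also concerns the SOC arm, yet its key comparison is labelled `SLS`, which looks like shorthand and not a decision to pool arms. Enrolment in a trial is moreover a coherent exposure for a Hawthorne question once the population is fixed. Finally, exact analysis sets are often left to the SAP, which was not available for this review.

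Much of this stands. A reader might infer that the sponsor meant to include RELVAR patients, or that ineligible and Greater Manchester patients are in the CPRD comparator. The documents do not support either inference. The statements of intent all point the other way, and 8.9 treats the Greater Manchester CPRD data as a separate, additional comparison.

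The reply does not dispose of the SLS part. The descriptive sentence sets one defined label against another, so shorthand for a source is a strained reading there. Sections 8.3.2 and 8.2.1 support the both-arms reading, and 8.5 counts all 2,800 enrolled and sets the CPRD minimum to match that number. Nor is this detail left to the SAP: the protocol itself fixes the pooled data sets and the exposure, and does so inconsistently with its objectives.

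**Conclusion.** The point holds as a contradiction in the specification of a co-primary analysis. Followed literally, 8.7.1 and 8.3.2 admit RELVAR patients to the PO2 and PO3 comparison, and the model has no term that would separate a RELVAR effect from the SLS region effect.

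The size cannot be derived from the document. Under an assumed 1:1 allocation the pooled SLS rate would be 0.90 to 1.05 times the SOC rate for assumed rate ratios of 0.8 to 1.1. At a rate ratio of 1 this bias is nil. These figures show the direction and rough scale of the bias path; they do not predict what the study will find.

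On the CPRD side the finding is limited to a label that should be aligned with 8.1, 8.2 and 8.2.1. It would be tempting to put a percentage on a diluted comparator rate. That would need assumed eligibility shares and event rates, and would ignore the model's covariates, which include previous exacerbation and medication group.

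**What to change.** In 8.7.1, name `SLS-SOC` and `CPRD-xGM-IC` in both the PO2 descriptive step and the multilevel model, and state that the same sets apply to PO3, SO1 and SO2. In 8.3.2, define the exposure for these analyses as the SLS SOC arm versus `CPRD-xGM-IC`. The PO1 label deserves the same check, since PO1 also names the SOC arm; randomisation makes pooling the arms largely harmless for baseline characteristics.

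The cost is wording in two sections and no new data. The Salford sample for PO2 and PO3 becomes the SOC arm only, as the objectives already state: 2,800 × 0.5 = 1,400 under an assumed 1:1 allocation, or 2,800 × 0.33 = 924 if SOC were a third. Section 8.5 should say which count applies.

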8.7. Data analysis

8.7.1. Essential analysis

All analyses will be conducted using SAS.

For PO1, distributions of the confounders and effect modifiers (as listed in Section 8.3.3) will be tabulated – summarised as proportions in each category for binary and categorical variables, and means/medians and standard deviations for continuous variables. Graphical visualisations will also be produced to aid interpretation (for example, boxplots to characterise age distributions in each population, stacked bar charts to visualise SES by population). This will be done for a series of the derived populations to separate out true differences in demographics in Salford and differences that arise as a consequence of data quality issues etc. The following comparisons will be of interest:

- CPRD-GM v CPRD-xGM: to give an indication of true demographic difference from the same data source.
- CPRD-GM-IC v CPRD-xGM-IC: as above, but restricted to patients meeting the inclusion criteria.
- SIR v CPRD-GM: to give an indication of differences arising as a consequence of selection bias of CPRD practices, and through data quality issues etc.
- SIR-IC v CPRD-GM-IC: as above, but restricted to patients meeting the inclusion criteria.
- SIR-IC v SLS-E: to give an indication of recruitment bias and physician researcher bias (at the approach stage).
- SIR-IC v SLS: to give an indication of recruitment bias (at recruitment stage).
- SLS v CPRD-xGM-IC: to indicate the difference between trial recruited, and those
 meeting the inclusion criteria outside of Salford. This is the key comparison for
 addressing PO1.

WWEpi Project number: PRJ2282

We will then move on to explicit modelling of regional variation of the characteristics within CPRD for the emboldened comparison (SLS v CPRD-xGM-IC) to ascertain whether the characteristics observed within Salford are unusual by comparison with CPRD-xGM-IC. We will take local authority regional level (anonymised) as the comparable unit to the study region for SLS. SLS will be considered unusual on a given demographic if an appropriately chosen summary statistic for that demographic (mean for continuous variables) falls outside the 2.5-97.5 percentile range.

For PO2, we will commence with exploratory analyses, similar to described above, to explore the distributions of the primary and secondary endpoints.

Hawthorne effect will be evaluated in two different ways.

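### PO2 judges SLS on an effect measured within its own strategic health authority, but words the conclusion as a comparison with the rest of the UK

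*Protocol*

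**What the plan says.** Protocol 8.7.1 (Essential analysis) fixes four elements of the PO2 decision.

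- **Hierarchy.** Patients lie within practices, and practices within "local authority region (with SLS members being treated as a single distinct region) -> strategic health authority region". SLS is therefore a region at the local-authority level, with a further level above it.
- **Upper level.** "Strategic health authorities (population threshold of 1 million) are non-anonymised (named) regions". The section does not say which of them holds SLS.
- **Quantity and threshold.** "We will then examine the random effect of the SLS region in the context of the random effects for the other regions". The trigger is met "if the random effect of the SLS region falls outside the 2.5-97.5 percentile range".
- **Conclusion.** If the trigger is met, "we will conclude that SOC SLS behaves unusually compared with the rest of the UK, and hence evidence of a Hawthorne effect".

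The rule is introduced as similar to the one for PO1 earlier in 8.7.1, which says: "We will take local authority regional level (anonymised) as the comparable unit to the study region for SLS". The PO1 rule compares a summary statistic with a percentile range and mentions no SHA level. Section 8.2 takes the CPRD group from the whole UK outside Greater Manchester. Section 8.7.1 carries the PO2 approach over to PO3, SO1 and SO2.

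**The concern.** In a nested random-intercept model, a local-authority effect is what remains after the effect of the SHA above it has been taken out. A region's departure from the UK mean is the sum of the two. The rule as written looks at the first and concludes about the second.

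The mismatch can run either way. A SLS region that is ordinary by UK standards can look low because its SHA is high. One that is extreme by UK standards can look ordinary because its SHA shares the departure. The rule decides a co-primary objective and is reused for PO3, whose results go to regulatory reporting (sections 5 and 11.2), so what the flag means should be settled beforehand.

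**Working it through.** The protocol gives no variance components, power or error rate for this rule, so there is no stated figure to reproduce. The 2.5 to 97.5 band corresponds to ±1.96 SD, or 5% in two tails, if effects are normal.

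**Model.** Region mean = μ + v + u, where v is the SHA effect, u the local-authority effect within its SHA, and the two are independent. Let s = var(v) / [var(u) + var(v)]. This share is assumed throughout, with a range of 10% to 50%.

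**Step 1: how far the two rules agree.** The rule on u flags |u| > 1.96 SD(u). The rule on the total flags |u + v| > 1.96 SD(u + v). Their correlation is corr(u, u + v) = √(1 − s). With effects known exactly, the bivariate normal gives:

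| SHA share s | √(1 − s) | Outliers on the total also flagged on u | Regions where the rules disagree |
|---|---|---|---|
| 10% | 0.949 | 70.5% | 2.95% |
| 20% | 0.894 | 58.2% | 4.18% |
| 30% | 0.837 | 48.8% | 5.12% |
| 50% | 0.707 | 33.8% | 6.62% |

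The last column is 2 × 5% × (1 − third column). At s = 0 the correlation is 1 and the rules coincide.

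**Step 2: a single region.** Suppose SLS lies exactly at the UK mean while its SHA lies 1.5 SHA-SDs above it. Then u = −1.5 SD(v), which in local-authority SDs is −1.5 × √[s/(1 − s)]. This is −0.50 at s = 10%, −0.75 at 20% and −1.50 at 50%. The judged effect is well below zero although SLS does not differ from the UK.

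**Step 3: estimated effects.** A simulation assumed 10 SHAs of 15 authorities each, precise authority means, known variances and 4,000 runs. It used predicted random effects and the percentile band of the other regions. SLS was given a local effect of −2 total between-region SDs.

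| SHA share | SHA +1.5 SD: u rule / total rule | SHA −1.5 SD: u rule / total rule |
|---|---|---|
| 10% | 50% / 37% | 63% / 71% |
| 20% | 56% / 28% | 67% / 78% |
| 30% | 63% / 23% | 70% / 83% |
| 50% | 77% / 14% | 82% / 92% |

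With no SLS effect both rules flagged about 6% to 7% of runs, and they disagreed in 2.5% to 7.7%. The rules do not differ in their overall false-flag rate. They differ in which regions they flag.

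**Step 4: where SLS sits.** If SLS were the only region in its SHA, u and v could not be separated for it, and the predicted local-authority effect would keep only 1 − s of its deviation: 90%, 80%, 70% or 50% at the four shares. With other authorities in the same SHA the loss shrinks. At s = 50% the retained share is 80% with 3 others, 92% with 10 and 96% with 20. The protocol does not say which situation applies.

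**The case against.** Three points on the other side have force.

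**Removing the SHA effect suits a Hawthorne question.** Section 6.2 describes changed behaviour by GPs and nurses in their practices during SLS, which is local. A difference shared with the wider health authority is not that, and netting it out is ordinary control for regional differences. The reference set is still local-authority effects from across the UK. When SLS shares an SHA, the local-authority rule is also the more sensitive one. For a local shift of 3 local-authority SDs with effects known, it flags Φ(3 − 1.96) = 85%. The rule on the total flags Φ(3/√(1 + r²) − 1.96), where r = SD(v)/SD(u): 77%, 67% and 56% at r = 0.5, 0.75 and 1.0. This stands. It is a reason to keep the local-authority effect, but not to describe it as a comparison with the rest of the UK.

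**The text may not fix the level.** Section 8.7.1 uses the word region for both levels, so a combined effect is not strictly excluded, and extraction details commonly belong in the SAP, which was not available. That is fair. But SLS is defined as a region only at local-authority level, and the mismatch between rule and conclusion is in the protocol text itself.

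**The model is not the only evidence.** Stratified SLS and CPRD comparisons and the before/after analysis (SO3) are also planned. These give context but do not change what the formal rule claims.

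A reader might go further and infer that a real Hawthorne effect would be absorbed by the SHA term and missed. The documents do not support that. It needs SLS to be alone in its SHA, which no section states; excluding Greater Manchester (8.2) produces that only if the SHA holds no other CPRD authorities. Even then the direction is open. Against a band of 1.96 true local-authority SDs, a shift of 3 SDs would be flagged in 69%, 48% and 26% at the same values of r. The actual band comes from shrunken estimates for other regions. If their reliability were 0.5 (assumed), the band would narrow by √0.5 and the figures would be 87%, 75% and 56%.

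**Conclusion.** The point holds as a mismatch between the quantity judged and the conclusion drawn. On the natural reading, the PO2 rule shows whether SLS departs unusually from its own SHA, relative to local variation across the UK. It does not by itself show that SLS is unusual against the rest of the UK.

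At assumed SHA shares of 10%, 20% and 50%, the rule catches about 70%, 58% and 34% of regions that are outliers on the total effect. These figures assume normal, independent and exactly known effects. The mismatch is modest if the SHA share is small and vanishes at zero.

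It would be too strong to say that the rule can never support a UK-wide statement, or that replacing it with the summed effect alone is plainly better. The first depends on a variance that the protocol does not give. The second would lose sensitivity to a purely local effect when SLS shares an SHA. The change is nevertheless worth making before analysis, because it determines what PO2, and through it PO3, SO1 and SO2, may claim.

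**What to change.** In section 8.7.1:

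1. State which SHA holds SLS, and that it must share it with CPRD authorities for its local-authority effect to be separable from the SHA effect.
2. Report two quantities for SLS, each against the same quantity for the other regions: the local-authority effect, and the total of SHA and local-authority effects.
3. Base any statement about the rest of the UK on the total effect.
4. Word the local-authority result as: compared with its own health authority, relative to local variation across the UK. It may be kept as the Hawthorne-oriented comparison.
5. Apply the same wording to PO3, SO1 and SO2.

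The cost is a few sentences and one extra summary of the same fitted model, with no new data. There will be two results instead of one, and they may differ. The reference band for the total effect is wider by a factor of √(1 + r²), which is 1.12 at r = 0.5 and 1.41 at r = 1.0, so that comparison has less power for a purely local effect.

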- PO1: To characterize the patients enrolled in the Standard of Care (SOC) arm of SLS COPD compared with the UK population of COPD patients (using the Clinical Practice Research Datalink (CPRD)), including distribution of SES/deprivation level, to evaluate the extent to which the SLS participants are representative of the UK patient population targeted for RELVAR. The comparator set will be specified on two bases: firstly, overall, and secondly, the subset fulfilling the protocol inclusion/exclusion criteria.
- PO2: To compare the rate of COPD exacerbation over the 12 months in Standard of Care arm of the SLS compared with the Standard of Care (SOC) recorded in the CPRD, in order to detect a potential Hawthorne effect.
- PO3: To compare the rate of serious pneumonia (defined by hospitalisation) over the 12 months in Standard of Care arm of the SLS compared with the Standard of Care recorded in the CPRD.

Secondary objectives:

- SO1: To make comparisons between the SLS SOC and the CPRD cohort on the following health care utilisation (HCU) endpoints: GP visits, hospital admissions, mortality and adherence.
- SO2: To evaluate other definitions of COPD exacerbations in SOC from CPRD.

WWEpi Project number: PRJ2282

 SO3: Self-controlled comparison of COPD and HCU endpoints in Salford before and after SLS commenced, using data from the SLS.

Study Design: Observational COPD cohort study, comparing Salford, UK (data source: SLS) with rest of UK (data source: CPRD) over a 12 month period.

Population: The setting is Salford, UK compared with rest of UK. The study population is, in Salford, participants recruited to the SLS and randomised to the SOC arm. In the rest of the UK, the comparison group is persons with COPD recorded in the CPRD who meet the eligibility criteria of the SLS.

Study Size: The target sample size for the SLS is 2,800. Study size in the CPRD will be based on the prevalence of COPD diagnosis codes; this will be a minimum 2,800 to match but is expected to be considerably larger (x5-10).

Analysis: Data analysis will use descriptive statistics for PO1. PO2 and PO3 will be addressed using multilevel modelling.

WWEpi Project number: PRJ2282

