SO1: To make comparisons between the SLS Standard of Care and the CPRD cohort on the following health care utilisation (HCU) endpoints: GP visits, hospital admissions mortality and adherence.

SO2: To evaluate other definitions of COPD exacerbation in SOC from CPRD.

SO3: Self-controlled comparison of COPD and other HCU endpoints in Salford before and after SLS commenced.

WWEpi Project number: PRJ2282

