8.3. Variables

8.3.1. Outcome definitions

Primary outcomes/endpoint:

Moderate/severe COPD exacerbations will be identified using an algorithm combining GP visits, prescriptions for oral corticosteroids and/or antibiotics, or hospital admission, as defined using information from study WEUSKOP5893. Rate of exacerbation during the 12 month follow-up will be calculated and compared with the SLS rate in the standard of care arm; if technically possible, exacerbation rates for the 12 months prior to index date (matched enrolment date) would also be compared.

• Pneumonia: To be defined as per the codelist in Table 1 (see 13.1).

Secondary outcomes/endpoints:

- Healthcare utilisation: All GP visits/encounters and all hospital admissions during the 12 month study period.
- Adherence to index prescription: Defined as percent days covered (PDC) and medication possession ratio (MPR) will also be calculated for the matched cohort, as well as discontinuation, switching medicine or adding on other medicines, to be compared with the SLS SOC arm.
- Deaths: All cause, pneumonia death, COPD-attributed death during the 12 month follow-up. For the CPRD, deaths will be determined using Office of National Statistics (ONS) linked mortality data.
- Other definitions of COPD exacerbation: Other definitions will be described as per the outputs of study WEUSKOP5893.

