8.3.3. Confounders and effect modifiers

- Sex
- Age
- Socio-economic status (SES)
- Current/SOC COPD Medication group:

WWEpi Project number: PRJ2282

- LAMA or LABA only
- o LAMA+LABA
- LABA+ICS (combination product or two inhalers)
- o LABA+ICS+LAMA
- Comorbidities
 - Cardio-and cerebrovascular diseases (heart failure, myocardial infarction, stroke)
 - o Depression
 - o Anxiety
 - o Asthma
 - History of pneumonia
 - Gastro-oesophageal reflux and peptic ulcer disease
 - o Diabetes
 - Charlson score (COPD will be removed from score)
- Markers of COPD severity
 - o Previous COPD exacerbation
 - FEV1 % predicted
 - FEV1/FVC ratio
 - GOLD stage
 - MRC Dyspnoea score
- Comedications: major medication classes for each comorbidity of interest
- Smoking
- BMI
- Vaccinations
- Disability status

Further information on the definitions for the variables above will be provided in the SAP.

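### The SO1 models for GP visits and hospital admissions hold no prior count of the same endpoint, so a standing difference in service use can be misread as a Hawthorne effect

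*Protocol*

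**What the plan says.** SO1 compares SLS standard-of-care patients with the CPRD cohort on "health care utilisation (HCU) endpoints: GP visits, hospital admissions mortality and adherence". Section 8.3.1 defines the utilisation outcome as "Healthcare utilisation: All GP visits/encounters and all hospital admissions during the 12 month study period"; it defines no count before index.

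For the multilevel models, section 8.7.1 states: "We will include all confounders and effect modifiers as covariates, with outcomes corresponding to the primary and secondary study outcomes", with one model per outcome, followed by backward selection on AIC. If the SLS region's random effect lies outside the 2.5 to 97.5 percentile range of the regional effects, the plan concludes that SLS standard of care is unusual and takes this as evidence of a Hawthorne effect. SO1 "will be carried out in the same way as PO2".

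The covariate list in section 8.3.3 includes "Previous COPD exacerbation" among the severity markers and "History of pneumonia" among the comorbidities. It leaves the definitions of the listed variables to the SAP, but not the list itself.

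The Abstract gives SO3 as "Self-controlled comparison of COPD and HCU endpoints in Salford before and after SLS commenced, using data from the SLS". Section 8.7.1 adds: "We will do the same thing within CPRD to control for UK-wide secular trends". It describes SO3 as a sensitivity analysis in support of PO2.

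**The concern.** The plan adjusts exacerbations (PO2) for earlier exacerbations and hospitalised pneumonia (PO3) for earlier pneumonia. For GP visits and admissions it has no counterpart, although a patient's past use of a service is an obvious predictor of later use.

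The two groups also enter differently. SLS patients are enrolled at their GP practice (6.1), whereas CPRD patients receive a randomly drawn entry date (8.1). Section 8.7.1 itself looks for recruitment bias under PO1. Habitual attendance may therefore differ before any study effect exists. Whatever the other covariates do not capture goes into the SLS region effect, which the rule then reads as Hawthorne. Stable differences between the other regions also widen the reference range, which can hide a real change.

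**Working it through.** **1. Outcomes against their own history in 8.3.3**

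| Outcome | Own history in 8.3.3? |
|---|---|
| PO2 exacerbation | Yes |
| PO3 hospitalised pneumonia | Yes |
| SO1 GP visits | No |
| SO1 hospital admissions | No |

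Age, Charlson score, comorbidities, severity and previous exacerbation are partial proxies, probably better for admissions than for GP visits.

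**2. What the rule does with a standing difference**

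The protocol states no power, effect size, visit rate or regional spread, so there is no figure to reproduce and every value below except the study size is assumed. Suppose there is no Hawthorne effect, the pre-existing rate ratio is RR, and regional effects are normal with log-scale SD τ. Then

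P(flag) = Φ(−1.96 − d) + Φ(−1.96 + d), with d = ln(RR)/τ.

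Example: RR = 1.2, τ = 0.10 gives d = 0.182/0.10 = 1.82 and P = 0.45.

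| RR | τ = 0.10 | τ = 0.15 | τ = 0.20 |
|---|---|---|---|
| 1.0 | 0.05 | 0.05 | 0.05 |
| 1.2 | 0.45 | 0.23 | 0.15 |
| 1.3 | 0.75 | 0.42 | 0.26 |

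**3. Percentile rule, without and with the prior count**

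Simulation with 140 regions of 100 CPRD patients (14,000 = 5 × 2,800, the lower end of the expected size in 8.5) and 1,400 SLS-SOC patients (half of 2,800). Assumed: mean 8 visits a year, patient log-rate SD 0.6, no Hawthorne effect. The count entered as log(count + 0.5), with 300 runs per setting. Entries are the percentage of runs flagged, without → with the count.

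| Regional SD, persistent / new | RR 1.2 | RR 1.3 | RR 1.4 |
|---|---|---|---|
| 0.10 / 0.05 | 6 → 1 | 59 → 13 | 96 → 23 |
| 0.10 / 0.10 | 12 → 7 | 32 → 9 | 62 → 15 |
| 0.15 / 0.05 | 1 → 4 | 15 → 9 | 53 → 13 |
| 0.15 / 0.10 | 4 → 7 | 16 → 7 | 41 → 12 |

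With RR = 1.0 the flag rate was at most 2% in either fit. At RR 1.2 the rates are lower than in step 2 for two reasons: observed region effects also carry sampling noise, which widens the range, and the SLS region was given the fixed shift without a persistent deviation of its own. The standard error of a rate near 4% is √(0.04 × 0.96/300) = 1.1 points, so the small rises in that column are near simulation noise.

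A second set-up used 150 regions of 93 patients, mean 6 overdispersed visits, regional SD 0.10, a |z| > 1.96 flag and a year-to-year correlation of about 0.42. It flagged a standing +0.20 log rate (ratio e^0.20 = 1.22) in 50 to 55% of runs without the count and 30 to 35% with it. At a correlation of about 0.21 the fall was only from 49% to 41%. The direction agrees; the size depends on the inputs.

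**4. Why adjustment is partial, and what overlap costs**

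With regression slope b on the log prior count, about b of a standing difference is removed and 1 − b remains. The slope was about 0.7 in the step 3 table. For RR 1.3 the remainder is 0.3 × 0.262 = 0.079, a ratio of 1.08.

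The same arithmetic applies to the effect sought. If study activity already covers a fraction f of the baseline window, about b × f of a practice-level Hawthorne effect is absorbed. With f = 0.5 this is 0.5 × 0.42 = 21% (taking b near the correlation of 0.42) or 0.5 × 0.7 = 35%. In the second set-up, with a true +0.20 log-rate Hawthorne effect:

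| Overlap with pre-index year | Flagged without count | Flagged with count |
|---|---|---|
| None | 49 to 51% | 52 to 76% |
| Half | 49 to 50% | 39 to 54% |
| Full | 46 to 51% | 20 to 38% |

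The true overlap is not in the document.

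**The case against.** The strongest reply is that SO3 already deals with this. It is a before/after comparison that covers the utilisation endpoints and uses CPRD to remove secular trends, so stable prior differences cancel. That is fair as far as it goes, and a careful reader would not rest a Hawthorne claim about GP visits on SO1 alone. But SO3 is a separate analysis, presented as support for PO2, and it changes neither the SO1 model nor the rule applied to it.

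SO1 is also worded only as a comparison. A reader might infer that the protocol gives SO1 a Hawthorne aim of its own. It does not; that reading comes only through the instruction to analyse SO1 as PO2. The leap from an outlying region to a Hawthorne effect is a weakness of the rule for every outcome, and a baseline count does not cure it.

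A reader might also infer that the counts are already extracted for SO3 and that adjusting costs nothing. Neither is supported. SO3 is anchored to the start of SLS, not to each patient's index date. Section 8.7.3 lists comparable extraction and the linkage lag as risks, and 8.3.1 offers even the pre-index exacerbation comparison only if feasible. Section 6.2 places the effect in GP and nurse behaviour during the study period, which for patients recruited later can begin before index. As step 4 shows, the loss can then be material. This part of the objection stands and shapes the fix.

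**Conclusion.** The point holds for GP visits and hospital admissions in SO1. The covariate list is fixed in the protocol, it omits the prior level of these two outcomes while including it for PO2 and PO3, and the rule gives a standing difference a causal label.

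The size cannot be taken from the document. Under the assumed inputs the prior count lowers false flags clearly at standing ratios of 1.3 to 1.4 and brings little or no gain at 1.2 under the percentile rule. It reduces the misreading and does not remove it. Nothing in the protocol shows that a standing difference exists; the point is that the model could not tell one from a study effect.

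A reader might expect the usual argument that baseline adjustment raises power, for example from 80% to 90% at a correlation of 0.5. That describes a patient-level comparison. The plan judges one region against the spread of other regions, so the figure does not apply. Priority is low to moderate, since SO1 is a secondary objective.

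**What to change.** - **8.3.3:** add the number of GP visits/encounters and the number of hospital admissions over a 12-month baseline window, derived in the same way in SLS-SOC and CPRD-xGM-IC.
- **8.7.1:** state that each SO1 utilisation model keeps log(count + 1) of the same endpoint, exempt from AIC selection, and that the SLS region effect is reported with and without this term.
- **Window:** take the 12 months before SLS commenced, in line with the SO3 before period. If the 12 months before index are used instead, state that overlap with study activity can absorb a material part of a practice-level Hawthorne effect, and rely on showing both fits.

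The cost is two derived covariates and a sentence or two in each section. SO3 needs utilisation records from before SLS in both sources, but the window must be fixed and the derivation aligned. A pre-SLS window has its own price: for patients recruited later it lies further from the outcome year, so it may predict less well, and some patients may lack records that far back. Reporting both fits makes either limitation visible.
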